7.2 Planned Analyses

We will test the hypotheses that: (1) stress enhances statistical learning (rmANOVA; facilitated reaction time for predictable items during learning in the Stress vs No Stress group); (2) stress enhances retention of statistical learning (*t*-test; better discrimination of *AB* category pairs in the Stress vs No Stress group); and (3) stress impairs episodic memory (*t*-test; overall lower exemplar recognition memory in the Stress vs No Stress group). Although there may be a global effect of worse episodic memory in the Stress group, we expect such deficits to be driven in part by an interaction with category type (*A*, *B*, or *X*). That is, if Stress potentiates statistical learning, these participants would quickly learn to anticipate the *B* category while viewing the preceding *A* category item. Thus, rather than focusing on encoding the *A* category item, they would be predicting the *B* category, leading to greater competition between encoding and statistical learning (rmANOVA; greater deficits in memory for *A* relative to *X* items in the Stress group).

For the fMRI experiment, we will investigate the neural mechanisms underlying stress effects on different forms of learning using a combination of *connectivity*, *multivariate*, and *univariate* approaches. Specifically, we will test the working hypothesis that stress will have opposite effects on neural processes supporting episodic encoding and statistical learning. Based on rodent models, we hypothesize that stress will facilitate the function of subregions and connections associated with the monosynaptic pathway (MSP) while impairing or sparing the function of the trisynaptic pathway (TSP).

We will test whether *stress induces state-level changes in TSP and MSP connectivity* by comparing background connectivity (Al-Aidroos et al., 2012) from CA1-entorhinal cortex (MSP) and CA1-CA2/3/DG (TSP) in Stress vs. No Stress participants. If state-level changes are not detected, we will use a different connectivity approach to separate connectivity patterns during different trial types. To probe the functional significance of connectivity changes, we will perform our recently developed seed connectome-based predictive modeling analysis ([name] et al., 2020), using whole-brain CA1 connectivity during encoding to predict subsequent memory performance in Stress and No Stress participants. To test whether *stress amplifies neural signatures of statistical learning*, we will use multivariate approaches to characterize neural evidence of prediction. Following prior work (Sherman & [name], 2020), we will train a classifier in the hippocampus (using a linear support vector machine implemented in Python's scikit-learn module) to distinguish between

Protocol Number [Protocol Number](#) Version Date and Version #

different scene categories. By training the classifier on voxel patterns in the hippocampus from the localizer run (in which no statistical regularities are present) to distinguish amongst B categories, we can derive a signature of B category to apply to learning runs. The extent to which B can correctly be classified during the preceding A item (when B has not yet been presented) serves as a neural measure of prediction. If stress amplifies neural signatures of statistical learning, we expect to see greater evidence for the predicted category in the Stress, relative to No Stress, group. Finally, univariate whole-brain analyses will include subsequent memory analyses (Wagner et al., 1998) (contrasting Remembered with Forgotten trials from conditions A/B/X) to *test how whole brain processes supporting memory differ* in Stress vs No Stress participants.

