1.1 Background

Stress is a serious and escalating public health issue, with average stress levels in 2020 significantly increasing in the US for the first time since national assessments began in 2007 (APA, 2020). High stress levels are linked to increased risk of adverse physical (Richardson et al., 2012; Booth et al., 2015; Gianaros et al., 2015) and mental (Sinha, 2001; Gruber et al., 2020; Vinkers et al., 2014) health outcomes spanning diagnostic categories. Although the influence of stress on the hippocampus, an important hub for learning, has been posited to play a crucial role in mental health outcomes ([name] & Sinha, 2018; Lee et al., 2002), this target mechanism remains poorly understood.

Advances in nonhuman animal research have revealed distinct stress effects across hippocampal subregions (Gould et al., 1998; Pavlides et al., 1993; Sapolsky et al., 1990; Chen et al., 2010; Ghosh et al., 2013; Gerges et al., 2001; McLaughlin et al., 2005; Pu et al., 2007). Intriguingly, these discrepancies map onto the trisynaptic (TSP) and monosynaptic (MSP) pathways of hippocampal transmission, with stress impairing the subregions involved in the TSP and sparing the subregions involved in the MSP. This suggests the novel hypothesis that stress will differentially impact learning processes supported by these pathways, impairing TSP-dependent while enhancing MSP-dependent functions. Recent work shows that these pathways make distinct contributions to different forms of learning, providing a unique opportunity to test stress effects across hippocampal pathways in humans.

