4.2.1 Primary Outcome Variables/Endpoints

To characterize how acute stress affects the relative expression of different kinds of memory, we will measure statistical learning and episodic memory. Statistical learning will be assessed using responses/response times during the learning task, as well as from memory tests (see above). Episodic memory will be assessed by recognition memory performance. We hypothesize that measures of statistical learning will be enhanced following acute stress (as measured, e.g., by greater response time benefits during learning) and that measures of episodic memory (e.g., later recognition) will be diminished following acute stress.

To identify the neural mechanisms by which stress influences these different kinds of memory, we will focus on hippocampal responses measured during fMRI scanning. We hypothesize that measures of functional connectivity between hippocampal subregions CA1 and CA3 will be lower following acute stress (consistent with poorer episodic memory),

Protocol Number [Protocol Number](#) Version Date and Version #

whereas functional connectivity between subregion CA1 and the entorhinal cortex will be higher following acute stress (consistent with better statistical learning).

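### The trisynaptic-pathway outcome is CA1-CA3 connectivity, expected lower, in 4.2.1 but CA1-CA2/3/DG, impaired or spared, in 7.2, and nothing says which governs

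*Combined protocol and SAP*

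**What the plan says.** **Measure.** Section 4.2.1, the primary outcome section, predicts that "functional connectivity between hippocampal subregions CA1 and CA3 will be lower following acute stress". Section 7.2 specifies the analysis and compares background connectivity "from CA1-entorhinal cortex (MSP) and CA1-CA2/3/DG (TSP) in Stress vs. No Stress participants". The region paired with CA1 there also takes in CA2 and the dentate gyrus. The monosynaptic-pathway (MSP) pair, CA1-entorhinal cortex, is the same in both sections. Its predicted direction is in 4.2.1: "functional connectivity between subregion CA1 and the entorhinal cortex will be higher following acute stress".

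**Prediction.** Section 4.2.1 says lower. Section 1.1 states the hypothesis as "impairing TSP-dependent while enhancing MSP-dependent functions". Section 7.2 first says that "stress will have opposite effects on neural processes supporting episodic encoding and statistical learning", and in the next sentence expects stress to help the MSP while "impairing or sparing the function of the trisynaptic pathway (TSP".

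**Fallback.** Section 7.2 adds: "If state-level changes are not detected, we will use a different connectivity approach to separate connectivity patterns during different trial types". The alternative approach is not named.

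**Status.** The Synopsis lists only performance on the behavioral tasks as primary and treats neural correlates as an additional outcome of the fMRI study. No alpha level, sidedness or multiplicity rule is stated anywhere.

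**The concern.** An outcome listed as primary should have one definition and one prediction, and here the TSP outcome has two of each. CA1-CA3 and CA1-CA2/3/DG use different sets of voxels and will give different values.

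The wording of the prediction matters more. If sparing is an acceptable outcome for the TSP, a report could present a non-significant group difference as agreeing with the hypothesis. The study's claim is that stress has divergent effects on the two pathways. A null TSP result shows no divergence by itself, and in a study of this size it cannot separate a spared pathway from an impaired one.

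**Working it through.** **1. The passages side by side.**
- 1.1: TSP function impaired. In that paragraph, sparing is said of the MSP subregions.
- 3.2: episodic encoding impaired.
- 4.2.1: CA1-CA3 connectivity lower.
- 7.2, working hypothesis: effects on the two processes are opposite.
- 7.2, next sentence: TSP function impaired or spared.
- 7.2, connectivity test: CA1-CA2/3/DG, no direction given.

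An unchanged TSP fits only the fifth of these. No sentence makes CA2/3/DG the stand-in for CA3, and none says what result would count as support.

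**2. The plan's own figure.** Section 7.1 gives 40 per group for d = 0.45 and 80% power. Assume two-sided 5%.
- One-sample or paired: ((1.960 + 0.842)/0.45)² = 38.8, so 39; the t-based calculation gives 41. The stated 40 lies between.
- Two independent groups: 2 × 38.8 = 77.5, so 78 per group; the t-based calculation gives 79.

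The stated 40 is therefore close to a within-group calculation and is not reproduced for Stress versus No Stress.

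**3. Power of the group comparison at d = 0.45.**
- Normal approximation, 40 per group: 0.45 × √(40/2) = 2.012; 2.012 − 1.960 = 0.052; power = Φ(0.052) = 52%.
- Noncentral t, 40 per group: 51.1%. The chance of a non-significant result is 1 − 0.511 = 48.9%.
- The Synopsis and 5.2 give N = 100 for the fMRI study. At 50 per group the t-based power is 60.6%, so 39.4% of such trials would be non-significant.

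Section 7.1 takes d = 0.45 from earlier evidence of statistical learning in the hippocampus. Applying it to TSP connectivity is an assumption.

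**4. If either region pair could be reported.** Let Z1 and Z2 be the two test statistics under no effect, with correlation ρ, each tested at two-sided 5% without adjustment.
- Either significant: 1 − P(both between −1.96 and 1.96).
- Either significantly lower: 1 − P(both above −1.96).

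| ρ (assumed) | Either significant | Either significantly lower |
|---|---|---|
| 0.95 | 6.5% | 3.2% |
| 0.9 | 7.0% | 3.5% |
| 0.8 | 7.8% | 3.9% |
| 0.5 | 9.1% | 4.5% |

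A single fixed measure gives 5% and 2.5%. Because one region contains the other, the upper rows are the more plausible.

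**The case against.** A reader might infer that both the measure and the success criterion are free to be picked after the data. The documents do not support that. Section 7.2 plans one TSP region pair, and no section plans a separate CA1-CA3 analysis. CA2/3/DG contains CA3, so 7.2 can fairly be read as the operational form of 4.2.1. The rates in step 4 therefore describe a choice that the plan does not offer. In the predicted direction they also stay below 5%.

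A reader might also infer that the TSP prediction cannot fail unless connectivity rises, so that with no true effect it would be met 97.5% of the time (1 − 0.025). That requires the sparing phrase to be a decision rule and non-significance to count as support. The phrase is a general expectation drawn from rodent models. The sentence defining the connectivity test gives no direction, and the only direction stated for TSP connectivity is lower. The adjacent promise of opposite effects would not be met by a null result, so *sparing* may be a drafting slip.

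Finally, the Synopsis limits how much weight *primary* can bear for the neural outcomes.

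These points stand and narrow the concern. They do not remove the differing region labels or the conflicting predictions, and no sentence elsewhere resolves either. The fallback in 7.2 is the one place where the plan explicitly lets the connectivity method depend on the result.

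**Conclusion.** The point holds as an inconsistency in the current text: an outcome under the primary heading has two region definitions and two incompatible predictions, with nothing to say which governs. It does not show that the plan intends to choose between them after the data.

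The practical weight lies in how a null TSP result may be read. At two-sided 5%, 40 per group and a true deficit of d = 0.45, about 49% of trials would be non-significant, so absence of significance cannot be offered as evidence of sparing. The false-positive figures of 6.5-9.1% (3.2-4.5% in the lower direction, against 2.5%) rest on assumed correlations of 0.95-0.5 and on a choice that 7.2 does not plan; they are illustrative. They count significance as success, whereas the null-result problem counts non-significance as success, so the two should not be combined.

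**What to change.** - Name CA1-CA2/3/DG background connectivity, which 7.2 already computes, as the TSP measure in both 4.2.1 and 7.2.
- State one prediction, lower in Stress than in No Stress, tested two-sided. Remove the sparing alternative in 7.2 or reconcile it with 1.1, 4.2.1 and the opposite-effects sentence.
- State that a non-significant difference supports neither impairment nor sparing.
- Label the fallback connectivity approach in 7.2 exploratory. Without this, aligning the region names still leaves the method dependent on the first result.
- A CA1-CA3 sensitivity analysis is optional, and only if the segmentation separates CA3. Section 4 mentions a T2 scan for hippocampal segmentation but does not say which subfields will be delineated.

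The cost is wording in two sections, with no new data. What is given up is the option of claiming a null TSP result as support.

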6.6 Locations/Facilities

Some behavioral studies will take place in Sheffield-Sterling-Strathcona (SSS) Hall ([name]) or [name] and some will be conducted online, on mTurk or Prolific.

The fMRI studies will take place in the FAS Brain Imaging Center in Dunham Lab ([name]) or BrainWorks ([name]).

7 Statistical Design

The general statistical approach involves examining differences in our outcome measures as a function of stress condition (i.e., whether participants experience acute stress prior to the learning task or not). Analyses will primarily be conducted with repeated-measures ANOVAs (rmANOVA) and t-tests where appropriate.

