7.1 Sample Size Considerations

For the behavioral studies, we aim for an $N = 46$ per condition. This is consistent with the sample size of the study on which this behavioral experiment is based (Sherman & [name], 2020).

To determine the sample size for the fMRI study, we conducted power analyses based on our previous work demonstrating evidence of statistical learning in the hippocampus (Sherman et al., 2020). These results indicate that we would need $N = 40$ participants per group to detect neural effects ($d = .45$, 80% power). Thus, we will recruit 80 participants and randomly assign them to Stress ($N = 40$) or No Stress ($N = 40$) conditions.

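### The trial-type connectivity analysis runs only after a null first test, and the plan gives it neither a secondary label nor error control

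*Combined protocol and SAP*

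**What the plan says.** Section 4.2.1 places hippocampal connectivity under the primary outcomes and gives each pathway a direction. For the trisynaptic pathway (TSP) it expects that "functional connectivity between hippocampal subregions CA1 and CA3 will be lower following acute stress". For the monosynaptic pathway (MSP) it expects CA1-entorhinal connectivity to be higher.

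Section 7.2 tests this by comparing background connectivity "from CA1-entorhinal cortex (MSP) and CA1-CA2/3/DG (TSP) in Stress vs. No Stress participants". The next step is conditional: "If state-level changes are not detected, we will use a different connectivity approach to separate connectivity patterns during different trial types". The plan does not name the second approach, list its trial-type contrasts, or define what counts as not detected (one pathway or both, and at what threshold).

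On inference, the opening of section 7 says only: "Analyses will primarily be conducted with repeated-measures ANOVAs (rmANOVA) and t-tests where appropriate". No alpha, sidedness, multiplicity adjustment or order of testing is given for connectivity. The exploratory label in section 7.2.1 applies to the cortisol and adrenergic covariate analyses and does not reach this step.

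**The concern.** The rule works in one direction. If the first comparison is positive, the second is not called for; if it is null, the second is run. The second step can therefore add a positive finding but can never weaken one.

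That would be harmless if the plan gave the second result a lower evidential status, or made both steps share one error allowance. It does neither, and the outcome is primary. A reader of the results could not tell from the plan whether a positive trial-type result after a null state-level result confirms Aim 2 or only suggests a hypothesis.

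**Working it through.** **Plan's own figure.** The plan gives no error rate for the connectivity tests, so there is none to reproduce.

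**Inputs**
- First-stage tests: 2, one per pathway (7.2).
- Fallback tests: number not stated. Base case assumed here: 1 per pathway.
- Alpha and sidedness: not stated. Assumed two-sided 0.05 per test (critical value 1.96), unadjusted.
- Correlation between the first-stage and fallback statistics in a pathway: not stated. Taken as 0 to 0.8.
- Pathways: assumed independent of each other.

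**Principle.** When no effect exists, running the second test only after a null first test gives the same chance of at least one false positive as always running both: P(first positive) + P(first null and second positive) = P(at least one positive). The figures over both pathways therefore do not depend on whether the trigger means one null pathway or two. The per-pathway figures take the trigger as applied to each pathway separately.

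**Per pathway, one fallback test:** p = 1 − P(|Z1| < 1.96 and |Z2| < 1.96)
- no fallback: 5%
- correlation 0: 1 − 0.95² = 9.75%
- correlation 0.5: 9.1% (bivariate normal)
- correlation 0.8: 7.8%

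**Both pathways:** 1 − (1 − p)²
- no fallback: 1 − 0.95² = 9.75%
- correlation 0.8: 1 − 0.922² = 15.0%
- correlation 0: 1 − 0.9025² = 18.5%

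The part due to the fallback is 15.0 − 9.75 = about 5 points, up to 18.5 − 9.75 = about 9 points. The step from 5% to 9.75% comes from having two unadjusted pathway tests.

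**If the fallback tested A, B and X separately.** The plan does not say this for connectivity; it names those conditions for the univariate analysis ("contrasting Remembered with Forgotten trials from conditions A/B/X"). With four tests per pathway:
- independent: 1 − 0.95⁴ = 18.5% per pathway; 1 − 0.95⁸ = 33.7% over both
- correlation 0.7 (simulation): 13.0% per pathway; 1 − 0.87² = 24.3% over both

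**Counting only results in the hypothesised direction** (same critical value, so 2.5% per test)
- no fallback: 2.5% per pathway; 1 − 0.975² = 4.9% over both
- one fallback test: 3.9% (correlation 0.8) to 1 − 0.975² = 4.9% (independent) per pathway; 7.7% to 9.6% over both
- A, B and X separately: about 13% to 18% over both

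**How often the fallback might be reached.** Section 7.1 gives d = 0.45 and 40 per group. A two-sided two-group t-test at 5% then has 51% power. With 50 per group (the N = 100 of section 5.2, split equally) it has 61%. If the connectivity effects were of that size, which the plan does not claim, a given pathway would still come out null 49% or 39% of the time. The branch is not remote.

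**The case against.** The strongest reply is that the fallback is good science written down in advance. The first comparison concerns a sustained state; the second separates trial types. Section 7.2 gives a reason to look there, because it expects the episodic deficit to depend partly on item category. The study is mechanistic, in healthy volunteers, and uses several neural approaches on purpose. All of this stands, and the trial-type analysis should be kept.

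A reader might go further and infer that the plan retests the same hypothesis, or goes on testing until something is found. The documents do not support either reading: the second question is different and finer, and the plan names one further approach and stops. Nor do they say that a null first stage would go unreported, or that a positive fallback would be presented as primary. Section 4.2.1 names the two connections but no trial-type contrast, so the fallback's status is undefined rather than declared primary.

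Two points about size also stand. The plan sets no 5% level that could be breached, so every figure here rests on an assumed alpha. And the hypotheses are directional, so about half of the two-sided false positives in a single test would contradict the claim.

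The point that remains is narrower. Disclosure alone does not control error. A primary outcome has a second route to a positive result, opened only by a null on the first, with no label or adjustment.

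**Conclusion.** The concern holds in this limited form: the step is legitimate, but its trigger and its evidential status are not controlled. Under the stated assumptions (two-sided 5% per test, independent pathways, one fallback test per pathway), the chance of at least one false positive rises from 5% to about 8-10% per pathway, and from 9.75% to about 15-19% over both.

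The range of about 24-34% over both pathways applies only if A, B and X are tested separately, and should not be quoted as the plan's error rate. It would also be wrong to attribute the whole excess over 5% to the fallback, since two unadjusted pathway tests already account for 9.75%.

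The direction of the effect is firm: the rate rose in every scenario examined, including the directional count. Its size is not firm, because alpha, the number of contrasts and the correlation between methods are all absent from the plan. This should be corrected before the connectivity data are analysed.

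**What to change.** In section 7.2:

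1. Name the two background-connectivity comparisons (MSP and TSP) as the confirmatory connectivity tests. State alpha and sidedness, and apply Holm across the two pathways. Designating one test per pathway without this would leave the 9.75% in place.
2. Name the trial-type method and list its contrasts. Run it whatever the first result, and report it as secondary or exploratory.
3. If the trial-type analysis is to support a primary claim, put it in the same Holm family, across both pathways and both methods.
4. State that a null first stage is reported as null.

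The cost is SAP wording and one extra analysis run, with no new data. A positive trial-type result then counts as secondary evidence.

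Holm across pathways also costs some power. At d = 0.45 and 40 per group (normal approximation), a single test has 52% power at 0.05 and 41% at 0.025, so the loss per pathway is at most 11 points. If both effects are real and independent, Holm gives 0.409 + (0.521 − 0.409) × 0.409 = 0.455, a loss of about 7 points. Putting four tests in one family costs more: 31% power at 0.0125, the strictest Holm step. That is a reason to keep the trial-type analysis secondary.
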